There will be no randomization. Study participants will be treated with deoxycholic acid (Kybella) 10 mg/ mL injected subcutaneously, targeting the medial thigh deep fat compartment (pre-fascial). Subjects will receive deoxycholic acid 2 mg/ cm², with injections of 0.2 mL spaced evenly 1 cm apart within the treatment area. Bilateral upper inner thighs will be treated. Each treatment will consist of a maximum of 8 mL (40 injection sites) of the study drug, with a maximum of 4 mL (20 injection sites) of the study drug for each thigh. All treatments will be performed by a study physician. Subjects will receive 1 to 4 treatment sessions, each spaced 6 weeks +/- 1 week. Treatment #2, #3, or #4 will be pursued if patient desires more treatment, and if there is sufficient fat for treatment, per investigator's judgment.

V. Study Procedures

a) Study visits and parameters to be measured
 All visits in this study will be performed at the UCSD Dermatology Clinic, 3rd floor,
 [name].

Screening/Baseline Visit (Visit 1, Day -14 to 1)

This visit is expected to take approximately 1 hour. The following describes the procedures performed at this visit.

Prior to any screening assessments, informed consent will be obtained by the
investigator. When the subject fully understands the nature of the study and its risks,
the subject will be asked to sign and date the informed consent form. The
investigator will then sign and date the form.

- 2. A detailed medical history of information pertaining to treatment will be obtained.
- 3. The investigator will perform a relevant physical examination.
- 4. Patient's weight will be obtained.
- 5. The subject will be asked to complete the Subject Self-Rating Scale (0 to 6 scale).
- 6. If the subject meets the criteria for the study, the subject will be assigned the next consecutive subject number.
- 7. Females of childbearing age will undergo a urine pregnancy test
- 8. The investigator will determine the patient's eligibility for the study.

First treatment (Visit 2, Day 1)

The treatment visit is expected to take approximately 1 hour. The first treatment may be combined with Screening/ Baseline.

Prior to Kybella treatment:

- 1. Patient will be asked to complete the Subject Self-Rating Scale, rated from 0 to 6.
- 2. Patient's weight will be obtained.
- 3. Concomitant medications and procedures will be confirmed and recorded.
- 4. The investigator will perform a relevant physical examination.

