- 5. Thigh circumference measurement will be obtained with anthropometric tape measure.
 - Thigh circumference will be measured at site of maximum bulge at Screening.
 Vertical distance of this site from the floor will be measured, such that thigh circumference measurements at all following study assessments are performed at the same site.
- 6. Caliper measurement of inner thigh skin-fold thickness will be obtained.

Caliper measurement will be performed at site of maximum bulge at Screening.
 Vertical distance of this site from the floor will be measured, such that caliper measurements at all following study assessments are performed at the same site.

- 7. Thigh gap measurement will be obtained.
 - Patient will be asked to stand with legs at a fixed distance apart. Measurement
 will be performed between sites of maximum bulge at Screening. Vertical
 distance of these sites from the floor will be measured, such that thigh gap
 measurements at all following study assessments are performed at the same sites.
- 8. Pre-treatment photographs will be taken.
 - Patients will be asked to stand with feet apart at a uniform distance.

 Anteroposterior and posteroanterior photos will be taken.

Treatment:

9. Deoxycholic acid (Kybella) 10 mg/ mL will be injected subcutaneously, targeting the medial thigh deep fat compartment (pre-fascial). Subjects will receive deoxycholic acid 2 mg/ cm2, with injections of 0.2 mL spaced evenly 1 cm apart within the treatment area. Bilateral thighs will be treated. Each treatment will consist of a maximum of 8 mL (40 injection sites) of the study drug, with a maximum of 4 mL (20 injection sites) of the study drug for each thigh. All treatments will be performed by a study physician.

Post-Treatment Phone Call #1 (Day 3)

Phone call expected to take 5-10 minutes.

1. Two days after treatment, patient will be called and asked to report adverse events since last treatment. All adverse events will be recorded.

Second treatment (+/-) (Day 36 to 50)

The treatment visit is expected to take approximately 1 hour.

Prior to Kybella treatment:

1. Patient will be asked to complete the Subject Self-Rating Scale, rated from 0 to 6.

- 2. Patient's weight will be obtained.
- 3. Concomitant medications and procedures will be confirmed and recorded.
- 4. Adverse events will be recorded.
- 5. The investigator will perform a relevant physical examination.
- 6. Thigh circumference measurement will be obtained with anthropometric tape measure.

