 Vertical distance of this site from the floor will be measured, such that thigh circumference measurements at all following study assessments are performed at the same site.

- 7. Caliper measurement of inner thigh skin-fold thickness will be obtained.
- Caliper measurement will be performed at site of maximum bulge at Screening.
 Vertical distance of this site from the floor will be measured, such that caliper measurements at all following study assessments are performed at the same site.
- 8. Thigh gap measurement will be obtained.
- Patient will be asked to stand with legs at a fixed distance apart. Measurement
 will be performed between sites of maximum bulge at Screening. Vertical
 distance of these sites from the floor will be measured, such that thigh gap
 measurements at all following study assessments are performed at the same sites.
- 9. Pre-treatment photographs will be taken.
- Patients will be asked to stand with feet apart at a uniform distance.
 Anteroposterior and posteroanterior photos will be taken.

Treatment:

10. Deoxycholic acid (Kybella) 10 mg/ mL will be injected subcutaneously, targeting the medial thigh deep fat compartment (pre-fascial). Subjects will receive deoxycholic acid 2 mg/ cm2, with injections of 0.2 mL spaced evenly 1 cm apart within the treatment area. Bilateral thighs will be treated. Each treatment will consist of a maximum of 8 mL (40 injection sites) of the study drug, with a maximum of 4 mL (20 injection sites) of the study drug for each thigh. All treatments will be performed by a study physician.

Post-Treatment Phone Call #4 (~Day 108 to 150)

Phone call expected to take 5-10 minutes.

1. Two days after treatment, patient will be called and asked to report adverse events since last treatment. All adverse events will be recorded.

Week 4 Follow Up (~Day 134 to 176)

Visit expected to take 1 hour. The visit will take place 4 weeks after the last treatment.

- 1. Patient will be asked to complete Subject Self-Rating Scale, rated from 0 to 6.
- 2. Patient will be asked to complete Post-Treatment Satisfaction Questionnaire.
- 3. Concomitant meds and procedures will be confirmed and recorded.
- 4. Adverse events will be confirmed and recorded.
- 5. Patient weight will be obtained.
- 6. A relevant physical exam will be performed by the investigator.
- 7. Thigh circumference measurement will be obtained with anthropometric tape measure.
 - Thigh circumference will be measured at site of maximum bulge at Screening.

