 Vertical distance of this site from the floor will be measured, such that thigh circumference measurements at all following study assessments are performed at the same site.
- 8. Caliper measurement of inner thigh skin-fold thickness will be obtained.
 - Caliper measurement will be performed at site of maximum bulge at Screening.
 Vertical distance of this site from the floor will be measured, such that caliper measurements at all following study assessments are performed at the same site.
- 9. Thigh gap measurement will be obtained.
 - Patient will be asked to stand with legs at a fixed distance apart. Measurement
 will be performed between sites of maximum bulge at Screening. Vertical
 distance of these sites from the floor will be measured, such that thigh gap
 measurements at all following study assessments are performed at the same sites.
- 10. Follow-up photographs will be taken.
 - Patients will be asked to stand with feet apart at a uniform distance.
 Anteroposterior and posteroanterior photos will be taken.

Week 12 Follow Up (~Day 190 to 232)

Visit expected to take 1 hour. The visit will take place 12 weeks after the last treatment.

- 1. Patient will be asked to complete Subject Self-Rating Scale, rated from 0 to 6.
- 2. Patient will be asked to complete Post-Treatment Satisfaction Questionnaire.
- 3. Concomitant meds and procedures will be confirmed and recorded.
- 4. Adverse events will be confirmed and recorded.
- 5. Patient weight will be obtained.
- 6. A relevant physical exam will be performed by the investigator.
- 7. Thigh circumference measurement will be obtained with anthropometric tape measure.
 - Thigh circumference will be measured at site of maximum bulge at Screening.
 Vertical distance of this site from the floor will be measured, such that thigh circumference measurements at all following study assessments are performed at the same site.
- 8. Caliper measurement of inner thigh skin-fold thickness will be obtained.
 - Caliper measurement will be performed at site of maximum bulge at Screening.
 Vertical distance of this site from the floor will be measured, such that caliper measurements at all following study assessments are performed at the same site.
- 9. Thigh gap measurement will be obtained.
 - Patient will be asked to stand with legs at a fixed distance apart. Measurement
 will be performed between sites of maximum bulge at Screening. Vertical

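### Do the printed Week 4 and Week 12 follow-up days, which fit only a four-session course, put the follow-up data at risk?

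*Combined protocol and SAP*

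**What the plan says.** Section IV.D sets the number and spacing of sessions: "Subjects will receive 1 to 4 treatment sessions, each spaced 6 weeks +/- 1 week". It gives the conditions for going on, "Treatment #2, #3, or #4 will be pursued if patient desires more treatment, and if there is sufficient fat for treatment", with the second condition left to the investigator's judgment. It does not say at which contact those conditions are assessed.

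Section V.a places session 1 on Day 1 and the optional sessions 2, 3 and 4 on Days 36 to 50, 71 to 99 and 106 to 148. Each session is followed two days later by a telephone call at which the "patient will be called and asked to report adverse events since last treatment".

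The follow-up headings read "Week 4 Follow Up (~Day 134 to 176" and "Week 12 Follow Up (~Day 190 to 232" (each range closes there). Under them stand the sentences "The visit will take place 4 weeks after the last treatment" and "The visit will take place 12 weeks after the last treatment". Both visits include the item "Patient will be asked to complete Post-Treatment Satisfaction Questionnaire", which is not listed at the session visits.

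Section VI.A names change in thigh measurements, photograph identification and satisfaction scores as secondary endpoints, without a time point. Section VI.B reports efficacy and satisfaction descriptively. Section V.c refers to a Schedule of Events that is not in the text available for this review.

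**The concern.** There are two strands.

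The first is a mismatch between headings and text. Each heading gives a single range of study days, while the sentence beneath it counts from the last treatment, which can be any of four sessions. Staff who scheduled from the heading would see a one-session subject for Week 4 some 133 to 175 days after the injection instead of 28. The labels can also collide: for a three-session subject, Days 155 to 176 fall in the Week 12 range by the sentence and in the Week 4 range by the heading.

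The second is the timing of the decision to stop. One condition for a further session is an investigator's judgment of remaining fat, and the first examination planned after an injection is at the next session visit. If a subject is found there not to need more treatment, the 4-week date has gone by. At stake would be the first of two satisfaction questionnaires, which serves the secondary objective in section II.A, and the comparability of values labelled Week 4. With only 15 subjects, a few such cases would be noticeable in a Week 4 table.

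**Working it through.** **Inputs.** Session 1 on Day 1 and the printed visit days (V.a); spacing of 6 weeks plus or minus 1 week, that is 35 to 49 days (IV.D); follow-up at 28 and 84 days after the last treatment (V.a).

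**Step 1: reproduce the printed days.** Session k falls between Day 1 + 35(k − 1) and Day 1 + 49(k − 1). This gives Day 1, 36–50, 71–99 and 106–148, as printed. Adding 28 to session 4 gives 106 + 28 = 134 and 148 + 28 = 176. Adding 84 gives 106 + 84 = 190 and 148 + 84 = 232. Both printed follow-up ranges are reproduced exactly.

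**Step 2: apply the sentence rule to every number of sessions.**

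| Sessions received | Last treatment | Week 4 (+28) | Week 12 (+84) | Days from end of range to printed start |
|---|---|---|---|---|
| 1 | Day 1 | Day 29 | Day 85 | 134 − 29 = 105; 190 − 85 = 105 |
| 2 | Day 36–50 | Day 64–78 | Day 120–134 | 134 − 78 = 56; 190 − 134 = 56 |
| 3 | Day 71–99 | Day 99–127 | Day 155–183 | 134 − 127 = 7; 190 − 183 = 7 |
| 4 | Day 106–148 | Day 134–176 | Day 190–232 | as printed |

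The printed days therefore describe a four-session course only.

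**Step 3: can the printed range be a scheduling window at all?** Take a four-session subject and measure the printed Week 4 range from that subject's own last injection. The extremes are 134 − 148 = −14 days and 176 − 106 = 70 days. For a subject treated on Day 148, the start of the printed range comes before the last injection. Even for four sessions, then, the range is the span of all possible due dates and not a window for one person. Only the sentence beneath the heading can be used to book a visit, and it gives one answer for each subject.

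**Step 4: the timing of stopping.** Assume that stopping is settled at the next session visit, 35 to 49 days after the last injection. The Week 4 date is then 35 − 28 = 7 to 49 − 28 = 21 days past, whether the subject stops after session 1, 2 or 3. Week 12 is still 84 − 49 = 35 to 84 − 35 = 49 days ahead.

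**Step 5: what would be lost.** Week 4 lists ten items: self-rating, questionnaire, concomitant medication, adverse events, weight, examination, circumference, caliper, thigh gap and photographs. Sessions 2 to 4 list nine of them, all but the questionnaire. The questionnaire is given again at Week 12, so at most one of its two administrations is missed or late.

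**The case for a change.** The best case for a change runs as follows. An approximation sign cannot absorb a gap of 56 or 105 days, so the headings are wrong for one- and two-session subjects. The telephone call two days after a session asks only about adverse events, so the next session visit is the first planned point at which remaining fat can be judged. The questionnaire appears only at Weeks 4 and 12, and no tolerance for either visit is visible. Clearer wording and one extra questionnaire page would cost little.

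The facts in that case stand: the printed days fit four sessions only, no tolerance is given, the time of the stopping decision is not stated, and the questionnaire is not listed at session visits. The inference to a needed change does not. A gap between heading and sentence does harm only if someone books from the heading, and step 3 shows that the heading cannot serve that purpose.

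The stopping scenario is one reading among several. A subject who does not want more treatment settles the matter at any time. The session visits are marked optional as a whole, which allows the reading that they take place only when treatment is already planned. The Schedule of Events might also settle the point.

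The extra page would gain little as well. A questionnaire completed 35 to 49 days after the last injection is 7 to 21 days late. It would count as a Week 4 value only under a tolerance of at least 7 days for the earliest such visit and 21 days for the latest.

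**Conclusion.** The arithmetic is certain: the printed follow-up days belong to a four-session course and miss the true dates for shorter courses by 7 to 105 days, measured from the end of the true range to the start of the printed one. This is a clerical matter. The rule under each heading is unambiguous and applies to any number of sessions, and no figure in the plan is miscalculated.

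The 7-to-21-day lateness is conditional. It arises only for subjects who stop after session 1, 2 or 3 and whose stopping is settled at the next session visit, which the available text does not say. How many of the 15 subjects that would be is unknown. The worst outcome is one questionnaire missed or late per such subject, with the second still due on time at Week 12. The plan has no Week 4 endpoint or test that could be biased, its summaries are descriptive, and neither the primary safety endpoint nor the Week 12 data are touched. Assuming injection and visit dates are recorded in the usual way, an analyst can compute the actual interval since the last injection and report Week 4 values with their true number and timing.

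Followed as written, the study reaches the same conclusions, so no change to the plan follows.

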- 11. Subjects with any known hypersensitivity to Kybella (deoxycholic acid) or any of the inactive ingredients: benzyl alcohol, dibasic sodium phosphate, sodium chloride, sodium hydroxide, hydrochloric acid
 - B. Source of subjects and recruitment methods
 Subjects will be recruited by flyers and handouts placed in the UCSD Dermatology
 clinic. Eligible patients will be determined from the inclusion and exclusion criteria.
 Eligible patients will be informed of the proposed study and its purpose and given the
 opportunity to ask any questions.

Standard HIPAA authorization to collect research data from the subject's medical record will be obtained at the time of informed consent.

C. Equitable Selection of Subjects

The risks and benefits of the research are fairly distributed among the populations that stand to benefit from it. Although the risk of this study is minimal, to be prudent, pregnant women will be excluded because of the potential harm posed to the fetus.

IV. Subject Enrollment

A. Number of subjects

15 subjects will be enrolled in the study.

B. Methods of enrollment

Subjects interested in participating in the study may contact one of the investigators. The study objectives, inclusion and exclusion criteria, possible risks and benefits of the study, and the information included in the informed consent form shall be discussed with prospective study participants. Subjects who believe they meet the exclusion and inclusion criteria and remain interested in the study shall be invited to come in for their screening visit. During the screening visit, the investigator will interview the subject and perform a simple clinical examination, particularly examining the thighs. Following the investigator's determination that the inclusion and exclusion criteria are met, the subject be invited to participate in the study.

C. Procedures for obtaining informed consent

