- b) Patient satisfaction related to study treatment:
 - i. Improvement in patient satisfaction, as measured by
 Subject Self-Rating Scale, a 0 (extremely dissatisfied) to 6
 (extremely satisfied) scale
 - ii. Scores on additional post-treatment patient satisfaction questionnaire

B. Statistical methods

This is a small descriptive study, with the primary safety endpoint of the incidence rate of patients who experience:

- 1) Any adverse event (AE) ascertained by patient report, physician evaluation, or laboratory value
- 2) One or more serious adverse events (SAE) as defined by CTCAEv4
- 3) Adverse events leading to study drug discontinuation.

The safety analysis will be based on the safety population, which is defined as all patients who have received at least one dose of study medication and who have had at least one post-baseline safety evaluation.

Adverse events will be explored for trends.

The efficacy analysis will be based on the intent-to-treat (ITT) population. In the ITT population, patients will be counted in the treatment group upon informed consent and completion of Baseline measurements, regardless of receiving any dose of study medication.

In the case of a subject's early termination from study, missing values will be imputed using last observation carried forward (LOCF) method.

Baseline values will be those values measured on day of screening, which may be combined with Day 1.

Reduction in inner thigh fat, as measured by tape measure and calipers, will be presented as change in millimeters or centimeters, and presented descriptively. Percent accuracy by three independent blinded physicians in correctly identifying baseline photographs, when comparing before-and-after clinical photographs of the treatment area, will be reported. Patient satisfaction scores on Subject Self-Rating scale and post-treatment patient satisfaction questionnaire will be presented descriptively.

VII. Risks and Discomforts

A. Complications of treatment procedure/drug side effects and toxicities

Deoxycholic acid will be injected subcutaneously in the treatment area by the principal investigator [name], or by a member of the study team who is a UCSD Dermatology resident physician, under direction of [name].

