APPENDIX II. Post-Treatment Satisfaction Questionnaire

1. Were you satisfied with the Kybella treatments you received for reduction of inner thigh fat?

Yes/No

2. Have you noticed a reduction in inner thigh fat, compared to prior to treatments?

No improvement

0-25% improvement

25-50% improvement

50-75% improvement

75-100% improvement

3. Would you recommend Kybella treatments to a friend interested in reducing inner thigh fat?

Yes/No

4. Considering the side effects and disadvantages, would you undergo Kybella treatment for reduction of inner thigh fat again?

Yes/ No

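### The satisfaction questionnaire has no score for a treated subject lost before Week 4, and LOCF cannot supply one

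*Combined protocol and SAP*

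**What the plan says.** Section II.A makes patient-reported satisfaction the secondary objective. Section VI.A gives it two endpoints: b.i, improvement on the Subject Self-Rating Scale (0 to 6), and b.ii, scores on the post-treatment questionnaire in Appendix II.

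In section V.a the questionnaire is item 2 of both follow-up visits: "Patient will be asked to complete Post-Treatment Satisfaction Questionnaire". For Week 4 the timing is "The visit will take place 4 weeks after the last treatment", and for Week 12 it is "The visit will take place 12 weeks after the last treatment". Neither the screening visit, nor any treatment visit, nor any post-treatment phone call lists it. The visit lists contain no early-termination assessment.

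On treatment, section IV.D says: "Subjects will receive 1 to 4 treatment sessions, each spaced 6 weeks +/- 1 week". Sessions after the first depend on the subject wanting more and on the investigator judging that enough fat remains.

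On missing data, section VI.B has one rule: "In the case of a subject's early termination from study, missing values will be imputed using last observation carried forward (LOCF) method". It sets the ITT population for efficacy and says satisfaction results will be described, but it names no population or denominator for the questionnaire.

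**The concern.** LOCF needs an earlier value of the same measure. Appendix II asks about treatments already received, so it can have no baseline version, and the plan does not collect it before Week 4. The plan therefore does not say how to count a treated subject who leaves earlier. The practical default is to leave that subject out.

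The people most likely to be left out may be the ones the form most needs. Item 4 asks: "Considering the side effects and disadvantages, would you undergo Kybella treatment for reduction of inner thigh fat again". A subject who withdraws because of pain, another side effect or lack of effect may well answer No to that item, and to items 1 and 3. If so, omitting such subjects pushes the reported percentages up. In an open-label single-arm study there is no comparison group in which the same loss would show.

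**Working it through.** **Nothing to reproduce.** The plan states no power, precision or dropout figure. Section IV.A says "15 subjects will be enrolled in the study", and section VI.B begins "This is a small descriptive study, with the primary safety endpoint of the incidence rate of patients who experience". The check is therefore a tabulation of visits, followed by bounds on a proportion.

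**Where each satisfaction measure is collected (section V.a)**

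| Contact | Self-Rating Scale (b.i) | Questionnaire (b.ii) |
|---|---|---|
| Screening | Yes | No |
| Before treatments 1 to 4 | Yes | No |
| Phone calls after each treatment | No | No |
| Week 4 after last treatment | Yes | Yes |
| Week 12 after last treatment | Yes | Yes |

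**Day of the first questionnaire.** With treatment 1 on Day 1 and spacing of 35 to 49 days, treatment k falls on Day 1 + 35(k − 1) to Day 1 + 49(k − 1). Week 4 adds 28 days.

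| Treatments received | Last treatment | First questionnaire |
|---|---|---|
| 1 | Day 1 | Day 29 |
| 2 | Day 36 to 50 | Day 64 to 78 |
| 3 | Day 71 to 99 | Day 99 to 127 |
| 4 | Day 106 to 148 | Day 134 to 176 |

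The last row matches the printed Week 4 window. Adding 84 days instead of 28 gives Day 190 to 232, the printed Week 12 window. A four-session subject has no questionnaire score for (134 − 1)/7 = 19 to (176 − 1)/7 = 25 weeks.

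**Chance that the gap arises at all.** Assume each of 15 subjects independently leaves before Week 4 with probability p. Then P(at least one leaves) = 1 − (1 − p)^15.

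| Assumed p | P(at least one) |
|---|---|
| 5% | 53.7% |
| 10% | 79.4% |
| 20% | 96.5% |
| 30% | 99.5% |

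**Effect on a Yes percentage.** Let x of 15 − d respondents answer Yes, with d missing. The observed figure is x/(15 − d). The figure for all 15 lies between x/15 (every missing answer No) and (x + d)/15 (every missing answer Yes). The values of x are illustrative.

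| d | Observed | Lower bound | Upper bound |
|---|---|---|---|
| 1 | 10/14 = 71.4% | 10/15 = 66.7% | 11/15 = 73.3% |
| 2 | 9/13 = 69.2% | 9/15 = 60.0% | 11/15 = 73.3% |
| 3 | 9/12 = 75.0% | 9/15 = 60.0% | 12/15 = 80.0% |
| 5 | 7/10 = 70.0% | 7/15 = 46.7% | 12/15 = 80.0% |

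The range widens by 1/15 = 6.7 percentage points for each missing subject. The tables treat all 15 enrolled subjects as treated.

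**The case against.** The case against giving this much weight is substantial.

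- **Satisfaction as a whole is not restricted to those who stayed.** A reader might infer that it is. But b.i is collected from screening onward, so LOCF has a value to carry for any leaver. This stands, and the point concerns b.ii only. The scale does not replace the questionnaire, because it rates the appearance of the thighs and does not ask about the treatment, recommending it or repeating it. For someone who leaves after one treatment, the carried value predates treatment, which is a separate weakness.
- **Stopping injections is not leaving the study.** Sessions 2 to 4 are optional, and a subject put off after one session can still complete the form at about Day 29. Only the follow-up visits are paid ($50 each, section IX), which favours attendance. This stands: only withdrawal or loss before Week 4 creates the gap. Someone who leaves between Weeks 4 and 12 has a score to carry.
- **No completers-only rule is written.** This also stands. The restriction follows from silence on the denominator.
- **The Schedule of Events cited in section V.c is not in the public text.** An early-termination form listed only there cannot be ruled out.
- **The size is assumed.** No dropout rate is given, and some leavers may be satisfied. It is tempting to set the bounds against the 73% satisfaction in the 15-patient pilot described in section I.B. That pilot used a different formulation on the hips and upper lateral thigh, and the plan sets no threshold. Sampling error alone is wide: the exact 95% interval for 9/12 is 43% to 95%.

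What survives is a measure that can be missing for informative reasons, with one missing-data rule that cannot act on it.

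**Conclusion.** The concern holds for the questionnaire endpoint. As the visit lists stand, a treated subject who withdraws or is lost before Week 4 has no score and LOCF cannot create one, so b.ii will in practice describe those who reached Week 4. An upward bias is plausible but conditional: it requires leavers to be less satisfied than stayers, and the documents do not show that they will be. With 3 of 15 missing and 9 of 12 satisfied, the result for all 15 could be 60% to 80%, and nothing in the plan requires that range to be shown.

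The consequence is modest, because the endpoint is secondary and descriptive and no test depends on it. The change is still worth making, since it is cheap and each missing subject matters at this sample size. The conclusion rests on the visit lists being complete.

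**What to change.** **Section V.a.** Unless the Schedule of Events already provides for it, have Appendix II completed at the last contact, in person or by phone, of any treated subject who ends participation before Week 4. Record the time since the last injection. Show item 2 (perceived fat reduction) from these early forms separately, because swelling, which section VII.A lists as a common side effect, may affect the answer.

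**Section VI.B.** For items 1, 3 and 4, report observed cases with the number missing. Beside that, give as a sensitivity figure the number answering Yes over all treated subjects, counting a missing answer as not Yes. All treated subjects is the suitable denominator because the ITT population can include undosed subjects, who cannot answer item 1. State that LOCF does not apply where no earlier questionnaire exists.

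**Cost.** A four-question form at one extra contact and one more column in a table. Early-exit answers will not be at the Week 4 or Week 12 time point, and subjects lost without contact will remain missing. The sensitivity figure is conservative, which is why it sits beside the observed-case figure and does not replace it.
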